Appendix J: AAOS Abstract February 2011

Appendix K: American Journal of Orthopaedics Article, 2015

1.0 Background

Over 13 million units of blood are transfused each year. While transfusion can certainly be life saving, numerous studies over the last twenty years have shown significant, dose-dependent increases in morbidity, mortality, and cost with each unit of packed red blood cells transfused. {Leal-Noval, 2001 #1} Transfusion is one of the most common interventions made in the critically ill population, however the negative effects of transfusion-related infection is well documented in recent literature. {Leal-Noval, 2001 #1;Leal-Noval, 2001 #1;Hebert, 1999 #2;Carson, 1999 #3;Edna, 1992 #6;Hill, 2003 #8;Vincent, 2002 #9;Taylor, 2002 #10} There is no question that transfusion of blood products can be life-saving to an acutely ill trauma patient, but there is little evidence to help the Orthopaedic Surgeon decide when a transfusion is indicated in an asymptomatic anemic patient who is no longer in need of acute resuscitation.

Several studies have analyzed healthy individuals with an isovolemic reduction in hemoglobin to a level of 5.0 (g/dL). {Leung, 2000 #16;Weiskopf, 1998 #17} They found no significant compromise in oxygen delivery to the tissues. Currently there is a lack of clinical data to suggest adequate red blood cell (RBC) transfusion endpoints in trauma surgery. {Johnston, 2006 #18} Given the lack of evidence to support transfusion triggers for young, healthy, asymptomatic Orthopaedic trauma patients, the purpose of this study will be to investigate the risk of complications associated with permissive anemia in this population.

Orthopaedic trauma patients treated at Eskenazi (previously Wishard) Hospital, a level 1 trauma center, are routinely allowed to be permissively anemic, or allowed to run as low as a Hemoglobin of 5 g/dL if they are young and healthy (see inclusion/exclusion criteria for objective definition) and asymptomatic from anemia. A retrospective review was performed using the inclusion/exclusion criteria proposed in this study to evaluate if a prospective study would be ethical and to provide a power analysis for number of patients needed to reject the null hypothesis. Over a 3 year period (2006-2009), 104 patients were identified who met the inclusion/exclusion criteria proposed in this study and were available for 1 year follow-up. This study controlled for Injury Severity Score, patient age, gender, and whether the patient had received multiple surgeries. We found that patients who were allowed to be permissively anemic (allowed to drop to a Hgb of 5 g/dL if asymptomatic at rest) had a lower complication rate ($p<0.01$) than those who were transfused to maintain a higher hemoglobin. Additionally, there appeared to be a dose-dependent affect ($p=0.02$) with higher complications seen in patients receiving multiple units of allogeneic blood. This data was presented at both the American Academy of Orthopaedic Surgery (2011) and Orthopaedic Trauma Association (2011) annual meetings and the manuscript is currently being reviewed for publication. This retrospective study does not prove causation of higher complication rates associated directly with transfusion, but does suggest there may be a lower complication rate in patients allowed to be permissively anemic. The largest barrier to publication of this retrospective study has been the repeated comments by reviewers that a prospective study is needed.

[name], Chief of Orthopaedic Trauma at Eskenazi Hospital, has met with the Chief of Anesthesia at Eskenazi Hospital, [name], and the Chief of Trauma for General Surgery, [name], to develop the inclusion and exclusion criteria listed

below so that this study might be completed in a multi-disciplinary approach with all providers agreeing to the inclusion and exclusion criteria and escape criteria listed below.

2.0 Rationale and Specific Aims

Transfusion of Orthopaedic trauma patients is routinely done in asymptomatic individuals as there is no accepted national standard or recommendations from the American Academy of Orthopaedic Surgeons or the Orthopaedic Trauma Association for what level of anemia is appropriate in an asymptomatic patient. Individual practitioners typically make this decision based on anecdotal experiences and expert opinion. No prospective study has been performed to date to answer this question in this patient population.

The null hypothesis of this proposed pilot study is that no difference will be seen with a liberal transfusion strategy to keep a patient's hemoglobin above 7 g/dL versus a conservative strategy to keep the patient's hemoglobin above 5.5 g/dL in patients asymptomatic at rest. The primary outcome of this pilot study will be infection; defined as postoperative wound infection (superficial or deep) or other perioperative infection but not surgical site (urinary tract infection or pneumonia). Deep infection is defined as the need for intravenous antibiotics or a return to surgery for debridement. Superficial infection is defined as the use of oral antibiotics only successfully treat a surgical site infection. Secondary outcomes will include pulmonary embolism, deep venous thrombosis, acute renal failure or insufficiency, nonunion, delayed union, compartment syndrome, osteomyelitis, nerve palsy, anoxic brain injury, cardiac ischemia or infarct, pancreatitis, or death, and the musculoskeletal functional assessment. These same outcomes were evaluated in the retrospective study done at this institution which found no difference within any one complication, but when all complications were pooled there was a higher complication associated with the liberal transfusion strategy.

3.0 Inclusion/Exclusion Criteria

Inclusion criteria:

- Trauma patients admitted to participating hospital with any Orthopaedic injury who have been determined to be stable by the Trauma Service (General Surgery) and are no longer within the resuscitation phase of initial treatment. This is defined as a normal urine output (greater than 0.5 ml/kg/hr) and a systolic blood pressure greater than 90 mmHg for greater than 6 hours without fluid bolus or transfusion during that time
- Age 18-50
- Hemoglobin less than 9 g/dL or expected drop below 9 g/dL with planned surgery

Exclusion criteria:

- Pregnant (urine pregnancy test will be done as standard of care)
- Prisoner
- Head injury (Glasgow Coma Scale less than 8 over 48 hours from presentation)
- Known cardiac (coronary artery disease, atrial fibrillation, stent placement, congestive heart failure), renal (acute or chronic renal insufficiency or failure,

defined as having Serum Creatinine >1.2 at time of enrollment), liver (Childs C cirrhosis) or pulmonary disease (chronic obstructive pulmonary disease, abnormal pulmonary function tests or history of poor pulmonary function from any cause including acute traumatic conditions such as ARDS)

- Unlikely to follow up in the surgeon's estimation
- Sickle Cell Anemia
- History of cancer
- Preexisting weakness, paresthesias, deformities, or other conditions which might affect functional outcome in the surgeon's opinion
- Spinal cord injury
- Patients with burns expected to require operative treatment
- COVID positive

4.0 Enrollment/Randomization

A consensus opinion was reached in a multidisciplinary manner with multiple members of the Trauma team (General Surgery), Anesthesia, Physical Medicine and Rehab, and the Orthopaedic Trauma Service. This team consisted of members from General Surgery ([name], [name], [name], [name]), Anesthesia ([name], [name], [name]), and Physical Medicine and Rehab ([name]) along with all members of the Orthopaedic Trauma Service ([name], [name], [name]) and the PI ([name]). The opinions in escape criteria and definitions will be referred to below as "consensus opinion". A biostatistician was consulted after he had reviewed the data from the retrospective study previously performed at this institution to help design an appropriately powered prospective randomized pilot study.

All Orthopaedic Trauma patients admitted to participating hospital will be screened for inclusion and exclusion criteria after they have been resuscitated and stabilized. The consensus opinion of the "stable" patient was defined as an awake and alert patient with normal urine output and systolic blood pressure greater than 90 mmHG for greater than 6 hours without fluid bolus or resuscitation. If a patient meets criteria for the study as noted above and is stable as defined above, the patient would be approached by either the Principal Investigator (PI) or a co-PI to determine interest and informed consent would be obtained for participation in the study. Patients who either refuse or are unable to consent will be tracked using the screening form. Enrollment would be performed in patients with a Hgb of 9 g/dL or less or in patients expected to drop below 9 g/dL with planned procedures or continued (controlled) bleeding. Randomization would not occur until the patient's Hgb dropped below 7 g/dL at which time a sealed envelope would be opened to determine if the patient would be randomized to a liberal transfusion strategy (transfuse to keep Hgb >7 g/dL) or a conservative strategy (transfuse to keep Hgb > 5.5 g/dL). If the patient's Hgb does not drop below 7.0 g/dL, randomization will not be done. Prior to starting enrollment, envelopes will be made by blinded personnel using a randomization list generated to assign subjects to receive treatment either after hemoglobin drops below 5.5 or after hemoglobin drops below 7.0. Randomization was

done with a block size of 4 to ensure the treatment allocation was balanced throughout the study recruitment period. Escape criteria have been established by the consensus group to allow transfusion in patients with clinical concerns for symptomatic or dangerous levels of anemia despite randomization arm (please see Escape Criteria outlined in section 5.0)

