5.0 Study Procedures

If the patient remains asymptomatic at rest (defined as no chest pain, shortness of breath, or dizziness), transfusion would be determined by randomization to the liberal transfusion strategy to maintain Hgb at 7 g/dL or the conservative transfusion strategy of 5.5 g/dL. After each unit of blood is transfused a Hgb level would be checked to ensure appropriate Hgb levels are maintained as well as routine clinical practice (typically daily Hgb levels drawn until at least 2 consecutive days show no further drop with no further procedures or bleeding expected). If the patient's Hgb does not drop below 7.0 g/dL, randomization will not be done but patient will still be followed and patient outcomes will be collected as part of a non-treatment group.

As noted in Section 4.0, a consensus group consisting of multiple physicians and the service chiefs from the Trauma Service (General Surgery), Orthopaedic Trauma Service, Anesthesia, and Physical Medicine and Rehab agreed to the following escape criteria to transfuse regardless of Hgb level or arm of randomization:

Escape Criteria

1. Patient has any of the following symptoms at rest: chest pain, shortness of breath, dizziness
2. Patient has a mean arterial pressure less than 50 mmHg that is not responsive to fluid resuscitation
3. At any time the patient's heart rate increases by more than 30% above baseline while under anesthesia
4. The patient's urine output drops to less than 0.5 mL/kg/hour and remains decreased despite adequate rehydration with fluids
5. Any objective evidence of cardiac ischemia including the following: EKG changes such as ST depression, an elevation of serum cardiac markers, a base deficit greater than 6, lactate greater than 2.5 that does not respond to fluid resuscitation
6. A decrease in systolic blood pressure by 10% or more with exercise (physical therapy) that does not improve with fluid resuscitation
7. Uncontrolled source of hemorrhage

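### Does the plan need a check for resting symptoms before the randomization envelope is opened?

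*Combined protocol and SAP*

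**What the plan says.** Section 1.0 places the question among patients without symptoms: it speaks of "transfusion triggers for young, healthy, asymptomatic Orthopaedic trauma patients, the purpose of this study will be to investigate the risk of complications". Section 2.0 sets a liberal strategy "versus a conservative strategy to keep the patient's hemoglobin above 5.5 g/dL in patients asymptomatic at rest".

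Section 4.0 defines a stable patient as "an awake and alert patient with normal urine output and systolic blood pressure greater than 90 mmHG for greater than 6 hours", without a bolus or resuscitation in that time. For an enrolled, consented patient the trigger is then hemoglobin: "Randomization would not occur until the patient's Hgb dropped below 7 g/dL at which time a sealed envelope would be opened". The only stated reason for not randomizing an enrolled patient is that hemoglobin never falls below 7.0 g/dL. The same section introduces escape criteria "to allow transfusion in patients with clinical concerns for symptomatic or dangerous levels of anemia despite randomization arm".

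Section 5.0 continues: "If the patient remains asymptomatic at rest (defined as no chest pain, shortness of breath, or dizziness), transfusion would be determined by randomization". The same three symptoms form escape criterion 1, which leads to transfusion at any hemoglobin level and in either arm. Neither the eligibility list in Section 3.0 nor the screening form in Appendix A has an item for these symptoms.

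**The concern.** The phrase *asymptomatic at rest* can be read in two ways. In Section 2.0 it can describe the people to whom the hypothesis applies. In Section 5.0 it decides whether the assigned arm directs transfusion. No step between the two confirms that a patient is free of symptoms when the envelope is opened, yet the verb in Section 5.0 presumes that starting state.

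If the phrase defines the population, the plan as written can randomize patients outside its hypothesis. Their first transfusion decision could not differ by arm, because escape criterion 1 would already apply. They would add to both arms without adding to the contrast. Removing them afterwards on the basis of the Appendix H escape form would not be a clean repair: that form also captures symptoms that first appear after assignment, so the exclusion would condition on a post-randomization event.

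**Working it through.** **1. The passages side by side**

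| Place | What it settles | Symptom condition |
|---|---|---|
| Section 3.0, Appendix A | eligibility | none |
| Section 4.0, stability | who may be approached | alertness, urine output and blood pressure only |
| Section 4.0, trigger | when the envelope is opened | none; hemoglobin below 7 g/dL |
| Section 4.0, last sentence | what overrides the arm | symptomatic anemia, after assignment |
| Section 5.0, opening | when the arm directs transfusion | no symptoms at rest |
| Section 5.0, escape criterion 1 | when transfusion ignores the arm | the same three symptoms |

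The operational rows do not conflict. Assignment follows hemoglobin. After assignment the arm governs while the patient has no resting symptoms, and the escape rule governs otherwise. A patient who is symptomatic at the trigger therefore has a defined path. Section 1.0 supports reading the phrase as part of a strategy, since it describes the retrospective cohort's permissive approach as "allowed to drop to a Hgb of 5 g/dL if asymptomatic at rest". Section 2.0 alone leaves both readings open.

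**2. The plan's own figures**

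Inputs from Section 8.0: 50 per arm, 95% confidence, expected rates of 30% to 50%, target margin of at most 14 points.

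Margin = 1.96 × √(p(1 − p)/50)

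- p = 0.30: 12.7 points
- p = 0.40: 13.58 points (stated 13.6)
- p = 0.50: 13.86 points (stated 13.9)

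These depend only on the number analysed and the rate. Patients symptomatic at the trigger stay in their arm, so 50 per arm remains 50 and the stated margins hold.

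**3. Worst-case dilution of the contrast**

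Let s be the share already symptomatic at the trigger, equal in both arms. The documents give no value, so 0 to 20% is an assumption. Ages 18 to 50 and exclusions such as "Known cardiac (coronary artery disease, atrial fibrillation, stent placement, congestive heart failure" and chronic lung disease make the low end more plausible. Suppose the arm makes no difference at all in these patients. The widest difference within the plan's range is 50% − 30% = 20 points, and it becomes 20 × (1 − s):

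| s | Patients per arm (50s) | Difference, points |
|---|---|---|
| 0 | 0 | 20 |
| 5% | 2.5 | 19 |
| 10% | 5 | 18 |
| 20% | 10 | 16 |

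The 95% margin for the undiluted difference is 1.96 × √(0.5 × 0.5/50 + 0.3 × 0.7/50) = 1.96 × √0.0092 = 18.8 points. A loss of 1 to 4 points is small beside that.

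The factor (1 − s) is a bound. Only the first transfusion decision is certain to be independent of arm; if symptoms resolve, the arm's threshold can govern later decisions.

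**4. Bias**

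Symptoms present before the envelope is opened cannot depend on what it contains. Such patients fall into the two arms by chance. An as-randomized comparison of two strategies, each with the same escapes, is unbiased for that contrast, and any dilution is part of the strategy effect being estimated.

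**The case for a change.** The best case for a change is that it is cheap and cannot be made later. One sentence in Section 2.0 or 4.0 and two form fields (randomization date and time, symptoms at rest) would turn symptom status into a baseline variable. Appendix H records symptoms only as a reason for transfusion, and no form in Appendices A to I has a randomization time. If patients were later dropped to match Section 2.0, there is almost no slack: at a 50% rate 49 per arm are needed for a 14-point margin, and 48 give 1.96 × √(0.25/48) = 14.1 points.

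Part of this stands. Section 2.0 does not say which reading applies, and recording status before the envelope would do no harm. The rest is weaker:

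- Appendices A to I do not record the assigned arm either, so they cannot be the whole randomization record. A missing time there does not show that it goes unrecorded. Appendix H does carry the transfusion time and the lowest hemoglobin before transfusion, so escapes can be set against the time of randomization if that is kept.
- Section 8.0 names no analysis set, but nothing in the plan provides for dropping symptomatic patients. The margins above 14 points arise only from an exclusion that nobody has planned.
- Making absence of symptoms an eligibility gate has its own costs. The judgment is partly subjective, dizziness above all, and would come just before an envelope drawn from blocks of 4, which invites selection. It cannot be made under anesthesia, although enrollment covers patients expected to drop with planned procedures. It would also create an unrandomized group with hemoglobin below 7 g/dL, which the plan does not describe: its non-treatment group consists of patients who never fall that low.
- A sensitivity analysis by baseline symptoms would rest on about 1 to 3 patients per arm at shares of 2% to 5% (50 × 0.02 = 1; 50 × 0.05 = 2.5). It could not alter any conclusion.

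**Conclusion.** This is a gap in wording that analysts can fill sensibly, and no change to the plan is needed. The observation is accurate: no symptom check is written at the trigger, and Section 2.0 leaves the role of the phrase open. But Sections 4.0 and 5.0 give a coherent rule that covers a patient already symptomatic at that moment. The natural analysis keeps everyone in the arm assigned and reports escapes descriptively.

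On that footing the per-arm estimates, which are the pilot's declared purpose, keep their stated precision. The between-arm contrast, which Section 8.0 says was not powered, loses at most 1 point of 20 at a 5% share and 4 points at 20%. Those shares are assumed, since the documents give none, and the loss is a worst case with no arm effect in the affected patients. The conclusion rests on an as-randomized analysis and on escapes being applied alike in both arms, as Section 5.0 directs. It would need another look only if the sponsor meant to exclude symptomatic patients after randomization, which no section says.

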Any adverse event identified by a member of the care or research team from any participating site will be documented in writing and the lead site principal investigator will be notified of adverse events as they occur. All serious adverse events, protocol deviations, and noncompliance will be reported to the IRB in accordance with IU IRB policies and procedures. Significant adverse events that meet the policy criteria will be reported to the IRB as they occur. All other adverse events will be documented and reported to the IRB at time of continuing review.

A Data Safety Monitoring Plan (DSMP) will be in place to compare provisional outcomes prior to final enrollment. Per the DSMP, an orthopaedic surgeon not involved with the study will serve as the reviewer, looking at study data for obvious trends in higher complications in one study group. Monitoring of data that has been collected from all participating sites will be done every 6 months and findings will be submitted to the IRB at the time of continuing review. The data safety monitoring board will be comprised of: [name]-Independent Orthopaedic Surgeon, practices at Methodist (Board Chair), [name]-Anesthesiologist at Eskenazi, [name]-General Surgeon at Eskenazi, and [name]- Biostatistician at Methodist. [name]- Assistant Research Professor of Orthopaedic Surgery at IU will provide statistical analysis as needed. The DSMB has the independent ability to stop the study at any time if there is a concern for patient safety.

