8.0 Statistical Considerations

Sample size:

This is a pilot study since the primary purpose of this study is to collect preliminary data on estimating the complication rates for orthopedic trauma patients who will receive blood transfusion either with a liberal transfusion strategy or a conservative strategy. The primary outcome of this study is whether a patient develops a complication while following a

conservative or liberal transfusion strategy for anemia. From our retrospective study, we anticipate the true complication rate would be anywhere between 30% and 50%. We want to estimate this proportion with 95% confidence and no more than 14% margin of error. With a sample size of 50 per group we would be able to reach this goal. For example, if the true proportion is 40%, the margin of error will be 13.6% and the maximum margin of error would be 13.9% when the true proportion is 50%.

Up to 370 subjects will be enrolled as part of the non-treatment group.

Data Analysis:

The primary endpoint is a dichotomous outcome, the presence or absence of a complication at post blood transfusion. A point estimate (sample proportion) and a 95% confidence interval for the proportion will be reported. This proportion will be computed for each of the two blood transfusion strategies. Although we did not power the study to detect a difference in complication rate between two strategies, we will compare the complication rates between two groups of patients. Descriptive statistics, like, mean, median, standard deviation for continuous outcomes will be used to describe the subjects' characteristics at baseline. Frequency counts and percent will be used for the categorical outcomes. Baseline clinical and demographic data will be compared between two groups to assess the effectiveness of the randomization. Dichotomous and ordinal variables will be examined using chi-square tests and continuous measures with Student's t-tests. Exploratory analysis will be performed to compute p-values which will be presented as an aid to evaluate the overall comparability of the treatment groups at baseline. Logistic regression model will be used to compare the complication rate or infection rate between two groups and baseline covariates will be included in the model if two groups are found to be significantly different in those covariates.

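### A single disclosed block size of 4 lets someone who sees the whole envelope series know, on average, one third of allocations in advance; varying the block size is a cheap improvement

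*Combined protocol and SAP*

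**What the plan says.** - **Block size.** Section 4.0 gives one value: randomization was "done with a block size of 4 to ensure the treatment allocation was balanced throughout the study recruitment period". It describes no varying block sizes, no stratification by site and no central allocation.
- **Concealment.** The envelopes are prepared before enrollment: "envelopes will be made by blinded personnel using a randomization list generated to assign subjects". Their opacity, numbering and custody are not described.
- **Trigger.** "Randomization would not occur until the patient's Hgb dropped below 7 g/dL"; only then is the patient's envelope opened. Consent comes first, at a hemoglobin of 9 g/dL or less or an expected fall below 9.
- **Visibility of the arm.** In patients without symptoms at rest, "transfusion would be determined by randomization to the liberal transfusion strategy to maintain Hgb at 7 g/dL", or by the lower threshold in the other arm (Section 5.0). The term open-label does not appear, but the team cannot apply a threshold without knowing it.
- **Entry.** The PI or a co-PI approaches patients (Section 4.0). Section 3.0 leaves two exclusions to the surgeon's judgement: likely loss to follow-up, and existing conditions that could affect function.
- **Sites.** Section 6.0 shows that there is more than one: "Any adverse event identified by a member of the care or research team from any participating site". Nothing says whether they share a list.
- **Size and analysis.** "With a sample size of 50 per group we would be able to reach this goal". Up to 370 more may be enrolled without being randomized. Section 8.0 also compares the two arms, including by logistic regression.

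**The concern.** With a known block size and visible arms, past allocations reveal future ones. The fourth envelope of each block is determined by the first three, and the third is determined whenever the first two match. Preparing envelopes blind protects the list, but it does not stop anyone counting.

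This matters only if someone who can anticipate the next envelope can also affect who receives it. Some room exists. Approach and the judgement-based exclusions come before consent, and a patient whose hemoglobin is already below 7 g/dL at consent can be randomized at once. To a lesser degree, the timing of hemoglobin draws could matter; that is an inference and is not stated in the protocol.

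At stake is the comparability of the arms. Section 8.0 adjusts only for baseline covariates on which the arms are found to differ significantly. That cannot correct selection on prognosis that was not measured. The conclusion in Appendix K gives the purpose of the prospective study as separating a direct effect of transfusion from transfusion as a marker of higher risk. Selective randomization would bring that confounding back.

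**Working it through.** **The plan's own figure.** Section 8.0 gives 95% margins of error for 50 patients per group. The formula is 1.96 × √(p(1−p)/50).
- p = 0.40: 1.96 × √(0.24/50) = 13.58%; the plan says 13.6%.
- p = 0.50: 1.96 × √(0.25/50) = 13.86%; the plan says 13.9%.

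Both reproduce. The sample-size arithmetic is not in question. The documents give no figure for predictability.

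**Inputs.** Block size 4 (Section 4.0). Two arms of 50 (Section 8.0), so 1:1 is inferred and 100 patients make 25 blocks.

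**Certain allocations, whole series observed.** A 1:1 block of 4 has 6 equally likely orders.
- AABB and BBAA make positions 3 and 4 certain: 2 each.
- The other four make only position 4 certain: 1 each.
- Mean = (2×2 + 4×1)/6 = 4/3 per block; (4/3)/4 = 33.3%, or 25 × 4/3 ≈ 33 of 100 patients.

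**Best guess (always the arm with more places left in the block).** The chance of being right at positions 1 to 4 is 1/2, 2/3, 2/3 and 1. The mean is 17/24 = 70.8%, against 50% with no information.

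**One series shared by two sites.** Assume that each envelope is equally likely to be used at either site, and that a site knows its position in the block but sees only its own allocations.
- Position 3 is certain if both earlier envelopes were its own (1/4) and match (1/3): 1/12.
- Position 4 is certain if all three earlier ones were its own (1/8), or exactly two were (3/8) and match (1/3): 1/8 + 1/8 = 1/4.
- Positions 1 and 2 are never certain. Mean = (0 + 0 + 1/12 + 1/4)/4 = 1/12 = 8.3%.

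**Alternatives.** Fixed sizes are enumerated. Mixed sizes come from 4,000 simulated lists of 100, with sizes drawn with equal probability and an observer who knows the set of sizes and every past allocation, but not the order of the sizes.

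| Blocks | Certain | Best guess right |
|---|---|---|
| Fixed 4 (plan) | 33.3% | 70.8% |
| Fixed 6 | 25.0% | 68.3% |
| Fixed 8 | 20.0% | 66.6% |
| Mixed 4, 6 | 5.5% | 69.2% |
| Mixed 4, 6, 8 | 2.3% | 67.9% |

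**Price in precision.** A truncated block of 8 can leave the arms 4 apart, and an abandoned block of 4 can leave them 2 apart. At 48/52 (4 apart), the margin in the smaller arm is 1.96 × √(0.25/48) = 14.1% at p = 0.50, just above the 14% target. At p = 0.40 it is 1.96 × √(0.24/48) = 13.9%, within it.

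**The case against.** The strongest answer is that a laboratory value, not a clinician, opens the envelope. Patients consent first, and if all 370 non-treatment places were filled, only 100/470 = 21% of enrolled patients would ever be randomized. At consent, staff often cannot know whether this patient will take an envelope, or which one. That stands. A reader might infer that investigators control who reaches randomization, and the documents do not support it. They support influence, most directly when hemoglobin is already below 7 g/dL at consent. Section 5.0 describes typically daily draws, which limits discretion over timing.

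A reader might also infer that nothing in the plan governs transfusion of an enrolled patient between 7 and 9 g/dL. That goes too far. Section 5.0 ties transfusion in asymptomatic patients to randomization and lists escape criteria. The Appendix H form offers only those criteria and a fall below the randomization threshold as reasons, and Appendix G records deviations. Neither Section 5.0 nor Appendix H, however, expressly covers a patient who is enrolled but has no assignment yet.

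The one-third figure is conditional, as the shared-series calculation shows. The trial is a pilot that is not powered for a difference, and mixed blocks barely lower guessing accuracy. These points limit the importance of the issue. They do not remove it, because Section 8.0 still compares the arms.

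**Conclusion.** The point holds as a cheap improvement. An observer who knows the block size, knows where blocks start and sees the full series is certain of 33% of allocations and guesses 71% correctly. If sites share a series and see only their own patients, certainty falls, to 8% for two equal sites under the stated assumptions. The documents do not say which applies.

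The consequence is a risk of selection bias in the between-arm comparison. Its size in any result cannot be estimated from the documents. Section 11.0 says that the team includes clinicians who prefer each strategy, and a reader might take this as evidence that allocation was steered. It is not: the preferences run in both directions, that section describes the wider group that agreed the protocol, and no manipulation is shown anywhere.

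**What to change.** For all unopened envelopes, issue a new list with randomly ordered, undisclosed block sizes (for example 4, 6 and 8), one list per hospital, held by someone outside recruitment. Remove the block size from the protocol version that recruiting staff use. Certain allocations fall to about 2%, but correct guesses only to about 68%, so the benefit is the near-removal of certainty.

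Reconcile Sections 4.0 and 5.0 with Appendix H so that the position of enrolled patients who are not yet randomized is stated.

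The cost is a new list, new envelopes and a possible end-of-study imbalance: up to 4 per site from a truncated block, plus up to 2 from an abandoned block of 4. These can add across sites and may take the smaller arm's margin of error just past 14%. If few envelopes remain unopened, the gain is small; report the fixed block size as a limitation instead.
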